
# 5.2 CARE AS USUAL (CAU)

VIPP-FC will be compared to usual care, as there is no pre-existing integrated care pathway for children in foster care. Care as usual varies widely from locality to locality and good data is not recorded that would currently allow precise specification of CAU in a planned trial. Systematically documenting CAU is therefore a key objective of this study. Initial consultations with CAMHS teams in our study sites, identified several likely treatments that may be offered within CAU: 1) Theraplay, 2) 1-3 sessions of foster carer consultation 3) network consultation, 4) Incredible Years, 5) foster carer support, 6) 6-12 sessions of psychotherapy, 7) behaviour support, 8) foster parent groups. As assessments of attachment disorders are rarely undertaken it is not possible to determine the extent to which the type and intensity of services offered to this particular group is different to other young children in foster care referred to CAMHS. We will use the Child and Adolescent Service Use Schedule (CA-SUS) to systematically describe and quantify the services received by children and carers in the comparator arm of the pilot trial, as well as detailed qualitative information from the scoping study (Phase 2b). The CA-SUS will ask participants to confirm whether they have attended any health services, mental health services, support services or childcare services and if so how many times they have attended these services in the last 6 months.

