behavioural signs of RAD that could indicate a potential RAD diagnosis. In-depth assessments of RAD will determine whether sufficient RAD symptoms are present for the child to enter the pilot trial. For the screening phase, active consent will be provided by the foster carer only, as it does not involve direct contact with the foster child. A letter will be sent to all parents explaining the study and offering them the opportunity to ask questions and opt-out if they have concerns. Parents will be given a minimum of two weeks to notify the Local Authority or the research team if they wish to opt out from the screening. If a child meets the RAD threshold full consent from those holding parental responsibility would then be obtained and the child and foster carer (if all parties are happy to proceed) will enter the pilot trial. Prior to randomisation, the child and foster carer will be invited to attend a baseline assessment and then randomised individually to VIPP-FC or CAU in a 1:1 ratio, stratified by age, gender and site. As this is a pilot trial 40 cases would be randomised in total, which is sufficient to test the feasibility questions described below and estimate approximate confidence intervals for key study parameters. VIPP-FC will be delivered in-home by trained CAMHS practitioners or other appropriately qualified VIPP-trained interveners. Baseline and end of treatment measures will include validated diagnostic assessments of RAD and co-occurring conditions, security of attachment (including disorganized attachment), sensitivity of parenting, child adjustment, carer wellbeing, and the CA-SUS measure of service use. In addition to these outcome measurements, we would also conduct qualitative interviews regarding carers' experiences of the programme and perceptions of VIPP among social workers and VIPP interveners. As a pragmatic study, we would aim to include as representative a group of children as possible and therefore we would aim to apply minimal exclusions based on comorbidity or type of foster care. The pilot RCT will allow us to:

- A. Test the feasibility of identifying sufficient numbers of appropriate cases through social care using appropriate screening instruments and diagnostic assessments of cases screening positively for RAD across several local authorities and locales (rural and urban).
- B. Test the feasibility of recruiting and consenting foster families with children with RAD to an RCT (numbers contacted, consented).

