### 5.1 INTERVENTION DESCRIPTION

Video-Feedback to Promote Positive Parenting (VIPP): VIPP is a brief home-based attachment and parenting intervention: it is highly acceptable to families, has a clear and empirically supported model of change and has strong evidence of efficacy with families of young children in many settings (Juffer, Bakermans-Kranenburg & van IJzendoorn, 2008). Staff that have received training in the intervention will visit families at home for six 90-min sessions over 4 months. Sessions 1 to 4 take place biweekly and focus on improving carer sensitivity to the child. Session 6 is a booster session, and can take place approximately a month after the 5th session and focuses on consolidating the information provided in sessions 1 to 4 and teaching carers sensitive discipline skills. Sessions involve both carer and child and start by video-recording carer-child interactions, which provides the basis for themed discussion in the next session. Themes include recognising the child's attachment signals and expressions, providing prompt and adequate responses to them, promoting empathy for the child, praising positive behaviour, and appropriate ignoring of negative behaviour. Carers are also given exercises and tips. Session content is consistent across families, although its presentation and the video feedback are tailored to the specific needs of each family. VIPP has recently been modified specifically for the foster care context by the developers of VIPP in the Netherlands. This modified programme (VIPP-Foster Care [VIPP-FC]) pays particular attention to the need to help carers recognise signals that are specific to foster children--that may be quite challenging and difficult to understand--so that they are better equipped to respond sensitively, and to support the child's secure attachment to them as their carer. VIPP-FC is thus designed to specifically address the attachment difficulties often shown by children in foster care. In particular, these children tend to demonstrate attachment signals that are very subtle, highly distorted or absent – e.g. not crying when hurt because they are not used to being comforted; becoming angry or fearful when comforted. By helping foster carers become aware of these subtle, distorted or absent signals and training them to respond appropriately, the child can learn that foster carers can be relied on in times of need and that it is safe to show their distress and seek comfort. For many children in foster care, their experience of physical interactions with carers has been extremely negative in the past, and hence VIPP-FC also specifically addresses how to gently and sensitively support the child's needs for physical contact and comfort (see Schoemakern et al., under review).

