# 8 END OF TRIAL

The study is planned to run for 30 months. Overall, participant involvement will be no longer than 6 months. The end of trial will be the last patient, last visit of phase 3 (pilot trial).

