# **13** TIMETABLE

The study is planned to run for 30 months. Phase 1 (4 months) will adapt and produce intervention manuals. In Phase 2 (6 months) we will train therapists, undertake initial feasibility testing and further examine key implementation parameters. Phase 3 (20 months) will be a pilot RCT, with 12-months for recruitment, 4 months for treatment and outcome assessment and 4 months for final analysis and dissemination. A GANTT chart is presented in Appendix 1. A summary of the key stages of the project is provided below:

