#### Phase 2b

6-12 months: run scoping study (Sep 2017 – March 2018)10-12 months: revise manual and protocol, complete ethics revisions (Jan 2018 - March 2018)

## Phase 3

11 months - 23 months recruitment for pilot trial (Feb 2018 - Feb 2019)

27 months: Complete final outcome assessment (June 2019)

27-30 months: Finalise analysis and submit final report (Sep 2019)

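### The CA-SUS looks back 6 months at an outcome visit about 4 months after baseline, so for services already in use the outcome count mixes about 2 pre-baseline months with in-trial use

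*Protocol*

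**What the plan says.** Section 5.2 explains that usual care varies between localities and that existing data do not allow it to be specified for a future trial. It concludes: "Systematically documenting CAU is therefore a key objective of this study". The CA-SUS is the quantitative tool for this in the comparator arm, supplemented by qualitative material from the scoping study. Its recall period is given once: carers are asked whether services were attended and "if so how many times they have attended these services in the last 6 months".

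The Phase 3 text in section 4.2 sets two measurement points ("Baseline and end of treatment measures will include validated diagnostic assessments of RAD") and lists the CA-SUS in that battery. The table of measures in section 7.2 also marks it twice, at baseline and at the later assessment. No other recall period is given for the second visit.

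The interval between visits has to be pieced together:

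- Section 5.1: trained staff "will visit families at home for six 90-min sessions over 4 months".
- Section 13: the pilot RCT allows "4 months for treatment and outcome assessment".
- Section 13, Phase 3 dates: "11 months - 23 months recruitment for pilot trial (Feb 2018 - Feb 2019" and "27 months: Complete final outcome assessment (June 2019".
- Section 8: "participant involvement will be no longer than 6 months".

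**The concern.** A recall period longer than the time since the previous interview makes the two windows overlap. Contacts in the last weeks before baseline are then reported twice, once at each visit. The outcome count no longer measures what the family received while in the trial.

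The data described do not allow the two parts to be separated. Section 5.2 asks for a number of attendances. Section 10.1 adds probing for missed services and for the nature of contacts with certain key services, but not their dates. An analysis plan could not undo the overlap afterwards.

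What is at stake is the level of usual care that families received during the trial, for services they were already using. That figure is one that the planners of a full trial would take from this study. Both arms are affected in the same way, so the overlap favours neither; it distorts the level of use and dilutes any change.

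**Working it through.** **Inputs**

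- Recall window: 6 months (section 5.2).
- Visits: baseline and end of treatment (sections 4.2 and 7.2).
- Treatment length: 4 months (section 5.1).
- Treatment plus outcome assessment: 4 months (section 13).
- Recruitment closes at month 23; last outcome assessment at month 27 (section 13, Phase 3).
- Participation capped at 6 months (section 8); target of 4 weeks from confirmed eligibility to baseline (section 6.2, Post-Screening Stage).

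**Step 1. The interval t from baseline to outcome.** From the Phase 3 dates, 27 − 23 = 4 months. This reproduces the 4 months stated in section 13 and matches the treatment length in section 5.1.

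**Step 2. Overlap.** Pre-baseline months in the outcome window = 6 − t. Share of the window = (6 − t)/6.

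| t (months) | Overlap (months) | Share of window |
|---|---|---|
| 4 | 2 | 33% |
| 4.5 | 1.5 | 25% |
| 5 | 1 | 17% |
| 6 | 0 | 0% |

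Only t = 6 removes the overlap. That would use the whole participation cap and conflict with the 4 months in section 13. If screening counts as participation, a 4-week wait (about 0.9 months) before baseline leaves at most about 6 − 0.9 = 5.1 months.

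**Step 3. What the counts can show.** Let B be the baseline count, O the outcome count and x the contacts in the overlap months. Those months lie inside both windows, so 0 ≤ x ≤ min(B, O). In-trial use is O − x, which therefore lies between max(0, O − B) and O.

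- B = 6, O = 6: anywhere from 0 to 6.
- B = 3, O = 3: anywhere from 0 to 3.
- B = 0, O = 4: exactly 4.

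The second case can be illustrated with a short course of foster carer consultation, which section 5.2 lists as likely usual care (1 to 3 sessions). One child has three sessions in the 2 months before baseline and none after. Another has three sessions 3 to 6 months before baseline and three more during the trial. Both give B = 3 and O = 3, yet in-trial use is 0 for one and 3 for the other.

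**Step 4. Converting to a monthly rate.** If use is steady, O/6 is the correct monthly rate. If use changes at baseline from r0 to r1 contacts a month, O = (6 − t) × r0 + t × r1. Take r0 = 1 and r1 = 2 as assumed values, so B = 6:

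- t = 4: O = 2 × 1 + 4 × 2 = 10. Rate 10/6 = 1.67 against a true 2, an error of −17%. Bounds are 10 − 6 = 4 to 10; true in-trial use is 4 × 2 = 8.
- t = 5: O = 1 × 1 + 5 × 2 = 11. Rate 11/6 = 1.83, an error of −8%. Bounds are 5 to 11; true in-trial use is 10.

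In the other direction, if use halved after baseline (r0 = 1, r1 = 0.5, t = 4), the ratio of outcome to baseline counts would be (2 + 4 × 0.5)/6 = 0.67, not 0.50.

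A change at baseline is plausible in either arm. Section 4.4 plans to recommend referral when another diagnosis warranting intervention is found, and the DAWBA for co-occurring diagnoses is given at baseline (section 7.2).

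**The case against.** The strongest reply is that the protocol does not fix the recall wording visit by visit. The sentence in section 5.2 describes the instrument in general, the form itself is not shown, and wording for each visit normally sits in the form. The CA-SUS is also openly a draft: adapting it is objective F in section 4.2, and section 10.1 describes testing and modification. Next, the visit interval is inferred, and any delay around treatment shortens the overlap. Finally, pre-baseline months are usual care too, so a 6-month count still describes its type and intensity; section 10 plans no service-use analysis; and equal windows give directly comparable counts.

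Part of this stands. The interval is an inference, and at 5 months the overlap falls to 1 month. The widest bounds need all overlap contacts to fall at one extreme. The 17% error rests on an assumed doubling of use at baseline. A referral for a newly found condition will often open a service with no baseline use, which the overlap does not touch. The consequence is small.

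The rest does not remove the point. The protocol states one window and gives no other for the outcome visit. The revisions listed in section 10.1 concern clarity and coverage of services, not the recall period. The purpose stated in section 5.2 is to quantify services received in the comparator arm of the pilot trial, and the outcome count as described does not isolate that for services already in use. The scoping interviews cannot recover an individual child's contacts during the trial.

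**Conclusion.** The concern holds as a minor refinement. If the stated window applies at both visits, and the visits are about 4 months apart as the timetable implies, a third of the outcome window precedes baseline and duplicates months already reported. At 5 months it is a sixth. For services in use before baseline, in-trial use can only be bounded. A monthly rate is correct only when use does not change at baseline. Services with no baseline use are unaffected.

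No feasibility test in section 10 and no progression threshold in section 13.1 depends on these counts. Confidence is medium, because both the visit interval and the use of the same window at the outcome visit are read from the protocol's general statements.

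**What to change.** Keep the 6-month recall at baseline. At the outcome visit, ask about use since the baseline visit, with that date given to the carer, and report contacts per month at each visit. For any parenting programme, also record the month it started and the month it ended.

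The cost is a change of recall wording at one visit and two date fields, in an instrument the study already plans to revise. The downside is unequal recall periods (6 months and about 4 months). Reporting monthly rates deals with the difference in length. With the window set to the time since baseline, the overlap is zero whatever the actual visit interval turns out to be.

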# 5.3 TRAINING

We will train a group of individuals from each NHS Child and Adolescent Mental Health Service (CAMHS) team involved in this study, as well as other appropriately qualified practitioners from other providers, in delivery of the VIPP-FC intervention. Each intervener will be trained by an accredited trainer, and will undertake supervised practice before becoming a study therapist. Accredited supervision will be provided to all practitioners during the pilot case series and feasibility trial.

# 5.4 TREATMENT FIDELITY

All therapeutic sessions will be audio recorded to enable assessment of fidelity by independent raters in 20% of sessions (tested using intra-class correlations, target ICC > .70). For every home-visit the practitioners will use a record form in which the goals and activities of the home-visit are described.

### 5.5 Setting

This project is a multi-site collaboration between 3 universities, 5 NHS Trusts and linked local authorities and takes place across two large and distinctive regions in England, Greater London and the Yorkshire and Humber region. As noted already, a substantial number of local authorities is necessary to ensure adequate recruitment and to capture important variability in organisational contexts that will be important to understand when preparing a future larger-scale clinical trial. The identification of children in foster care with RAD will be supported by a screening mechanism run by the local authority in collaboration with the university. If necessary additional support will be offered to the Local Authorities to do follow-up phone calls to foster carers by a member of the local CRN or the research team with appropriate honorary contracts. Also, during routine appointments, social workers will seek verbal consent from foster carers to pass on their contact details to the research team so that they can contact them directly to follow-up completion and return of questionnaires. Once potential participants have been identified by the screening process and indicated their interest in taking part by returning the initial questionnaires and consent form or completing the online consent form and online questionnaires, the assessment of eligibility will be undertaken by the research team through an in-depth assessment conducted in the participants' homes. After randomisation the clinical intervention will be delivered by practitioners from one of the participating intervention teams. Below we provide further contextual information regarding each of the sites:

North East London Foundation NHS Trust (NELFT): NELFT provides care to a population of around 1.75 million people. The CAMHS services provide support for looked after children in the local authorities of Barking, Havering, Waltham Forest and Dagenham, and will shortly extend to Essex (providing scope for additional recruitment sites for this study if necessary). The research is strongly supported by the Interim Medical Director and its Research Director is a co-investigator ([name]). There are approximately 120 children in foster care under 7 (excluding Essex, which has a similar number).

*Central and North West London NHS Foundation Trust (CNWL)*: CNWL provides care across a broad span of North West London, and beyond London. It employs approximately 7,000 staff to provide more than 300 different health services across 150 sites and in many other community settings. It provides CAMHS services across five London boroughs and to Milton Keynes. There are well-established links between CAMHS and social care in each of these settings, including specialist Looked After Children services. The local authorities covered by CNWL have approximately 250 children in foster care aged under 7.

South London and Maudsley NHS Foundation Trust (SLaM): SLaM provides a full range of mental health services to the people of Croydon, Lambeth, Southwark, and Lewisham as well as national specialist services. It has a budget of £290 million. The service is made up of five clinical units: National & Specialist, with a national & international reach and the local South East London boroughs of Lambeth, Southwark, Lewisham and Croydon. South London and Maudsley NHS Foundation Trust has the largest child and adolescent mental health service in the country. The local authorities have approx. 250 children in foster care aged under 7.

*Tavistock and Portman NHS Foundation Trust (TPFT)*. TPFT provides CAMHS services for Camden and Haringey Local Authorities in north London. The Haringey First Step service uniquely provides psychological screening for *all* looked after children in Haringey. The Tavistock has an active collaboration with the developers of VIPP at the University of Leiden and is the leading UK centre for VIPP training. Currently there are approximately 450 LAC in Haringey and around 100-150 are under 7 years.

*Leeds and York Partnership Foundation NHS Trust (LYPFT*) provides services for City of York local Authority (population 200,000) and North Yorkshire Local Authority (population 600,000). LYPFT runs in-patient and specialist CAMHS, while community CAMHS is run by Tees Esk and Wear Valley (TEWV) Trust. LYPFT has excellent links with TEWV and if needed TEWV could also be engaged in the study. These two authorities have around 120 children in foster care under 7 year.

# 6 SAMPLING AND RECRUITMENT

### 6.1 STUDY SAMPLES

#### Pilot Intervention Series

For *Phase 2a*, the pilot case series (non-randomised), we aim to recruit 6 cases for piloting the clinical intervention in a systematic case-series. Recruitment for this pilot case-series will also provide an opportunity to pilot the screening process that would operate on a larger scale in phase 3. Specifically, we will work with up to two of the Trusts for this initial pilot screening and case-series. As noted above, cases would be screened using screening instruments, and we propose to include a mixture of cases meeting RAD diagnostic criteria and some falling just short of this threshold in order to explore whether the intervention requires adjustment for both of these groups of children, and to maintain the pace of manual development in the event that prevalence is lower than expected.

#### Qualitative Scoping Study

For *Phase 2b* (the feasibility scoping study) we will conduct qualitative interviews and scrutinise documentary data sources in collaboration with participating local authorities and CAMHS services. Qualitative interviews will involve local authority children's services managers (N=3), CAMHS managers (N=3), social workers (N=3), foster carers (N=3) and parents (N=3) across the two geographical locations (N=24 interviews in total). These stakeholders will be purposively chosen to reflect the range of different service contexts so that findings will be as generalisable as possible, and it is anticipated that this sample size will capture a diverse range of views without necessarily reaching data saturation.

#### Pilot RCT

For Phase 3 (the pilot RCT) we will again undertake a screening process to identify children in foster care with RAD. We will then randomise 40 children (and their carers) to receive either VIPP (plus care as usual) or care as usual only. Based on data obtained from the Department of Education from 2014 (which we have corroborated against a selection of figures obtained in 2016 from our participating local authorities) we expect the full population of children in foster care in our target age groups across sites to be in the region of 700. Previous research experience with this population and on the basis of our small pilot screening, we would expect more than 80% of foster carers to take part in the initial screening and return the questionnaires. This estimate seems reasonable, since in the study of Green et al. (2014) of 523 foster families who were approached, only 56 refused (a further 57 were ineligible). Conservatively therefore we will aim for a sample size for the screening stage of 500. In order to identify cases likely to be diagnosed as RAD we will choose cases above the highest 66th percentile for symptoms of RAD (initially based on normative data), leading to a sample size of 150 who would be invited to take part in a more in-depth assessment. We expect a minimum of two thirds of those to agree to take part and complete the assessment. In the randomised controlled trial of the Fostering Changes programme, (Briskman et al., 2012) 77/125 took part in the intervention (following a higher rate of initial interest and questionnaire return), so two-thirds agreeing to an initial assessment is a conservative estimate. From this pool of 100 children we would therefore have scope to identify at least 40 cases that would be eligible for treatment as long as the prevalence of RAD in the high-scoring screened group was 50% (allowing for a further 10% dropout at this stage). Note that we would seek to obtain consent to treatment at the in-depth intake assessment stage, which is why we estimate the throughput of cases to be lowest at this point. As noted already, we lack reliable information concerning the prevalence of RAD in UK foster care and so the 50% prevalence within the population of children exceeding the symptom threshold is subject to uncertainty. Consequently, we propose an interim analysis after 15 cases have been assessed to establish whether the proportion of RAD cases is below this expected proportion. The lower bound of the 95% confidence interval around a proportion of .50 is .22 with a sample size of 15. Thus, identification of fewer than 3 cases out of 15 would suggest that the prevalence is lower than .50. In this event, we propose to widen the eligibility criteria to include children scoring over the screening threshold, but not meeting full RAD diagnostic criteria.

The sample size targets above are reasonable based on considerations of the level of precision with which we can identify key feasibility parameters, in particular the proportion of participants successfully consented (of those identified/approached) and the proportion of participants successfully completing the post-treatment outcome assessments (of those randomised), which we view to be key feasibility questions. A sample size of 40 provides a reasonable balance between precision and cost. Assuming the proportion of

participants successfully completing the key outcome assessment is 75% (30/40; note that in the Fostering Changes trial this figure was 80%), then this yields a 95% CI of 59% to 87%. The consent/up-take rates will be estimated at two stages – for consent to take part in the eligibility assessment, and following eligibility, the proportion entering treatment/being randomised. The former will be estimated with higher precision as they are based on larger samples. Assuming 67% (100/150) take part in the eligibility assessment, this yields a 95% confidence interval of 59% to 74%. Similarly, assuming that 80% of cases identified with RAD (40/50) go on to be randomised, we would obtain confidence intervals around that proportion of 66% to 90%.

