#### Child:

- (a) living with foster carer(s) in a placement planned to be at least 4 months;
- (b) lived with foster carer for at least 4 weeks
- (c) presence of DSM-5 defined RAD\*
- (d) aged between 11 months and 6 years

Note: as outlined below, because of the uncertain prevalence of RAD in UK foster care populations, the RAD eligibility criterion will be reviewed after 15 cases have been assessed. If fewer than 3 (out of 15) cases scoring over the screening threshold (> 66th percentile on screening measure) actually meet diagnostic criteria, we propose to include sub-diagnostic cases with elevated symptoms in the feasibility trial based on the screening threshold (defined below).

For the pilot case series, we will include a mix of cases that meet the RAD diagnosis and those falling short of the diagnostic threshold in order to explore the suitability of the intervention for both groups of children and expedite the rapid progress of manual refinement.

\*If during the RCT phase number of participants deemed eligible is inadequate to allow delivery of the final study aim (i.e. run the modified VIPP programme for foster care) we will expand the eligibility criteria to include carers with children who do not necessarily meet the RAD criterion.

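### The interim trigger of fewer than 3 RAD cases in 15 is one case stricter than the protocol's own lower bound of .22 implies

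*Protocol*

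**What the plan says.** Section 6.1 (Pilot RCT) builds its recruitment funnel on 100 in-depth assessments: "From this pool of 100 children we would therefore have scope to identify at least 40 cases", provided that half of the assessed group has RAD and "allowing for a further 10% dropout at this stage". Because UK prevalence is uncertain, "we propose an interim analysis after 15 cases have been assessed to establish whether the proportion of RAD cases is below this expected proportion". The basis for the cut-off is: "The lower bound of the 95% confidence interval around a proportion of .50 is .22 with a sample size of 15". The next sentence draws the rule: "Thus, identification of fewer than 3 cases out of 15 would suggest that the prevalence is lower than .50". If it is met, children over the screening threshold but short of a full diagnosis become eligible.

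Section 4.4 repeats the rule among the child inclusion criteria: "If fewer than 3 (out of 15) cases scoring over the screening threshold" meet diagnostic criteria, sub-diagnostic cases are to be admitted. A footnote in the same section allows eligibility to be widened during the RCT phase if too few children qualify. It gives no number and no time point.

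**The concern.** The cut-off is presented as a consequence of the .22 bound, but the two do not agree. This is the only numerical trigger for widening eligibility, and it stands in the eligibility criteria as well as in the sample size section, so the study would act on it. A trigger stricter than its stated basis makes the study slower to react when prevalence is below the level that the funnel assumes. The two cut-offs give different decisions only when exactly 3 of the 15 children are diagnosed. That is a plausible count at the prevalences the look is meant to detect.

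**Working it through.** **Inputs (Section 6.1).** Expected prevalence .50; interim n = 15; stated lower bound .22; written rule X ≤ 2; assessed pool 100; target 40 randomised; loss after diagnosis 10% in the funnel paragraph, 20% in the precision paragraph ("assuming that 80% of cases identified with RAD (40/50) go on to be randomised").

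**1. The stated bound.** The standard error is √(.50 × .50 / 15) = .1291. With the t quantile on 14 degrees of freedom (2.145), .50 − 2.145 × .1291 = .223, so the protocol's .22 reproduces. Other methods give .247 (Wald with the normal quantile), .214 (Wald with continuity correction), .274 (Wilson), and exact limits of .213 at 7/15 and .266 at 8/15. All exceed .20.

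**2. From bound to count.** .22 × 15 = 3.3. The largest whole count below 3.3 is 3, and 3/15 = .20 < .22. The rule that follows is X ≤ 3.

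**3. Exact check at prevalence .50.**

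| Count x | P(X ≤ x) at .50 | Exact upper 95% limit for x/15 | Excludes .50? |
|---|---|---|---|
| 2 | 121/32768 = 0.4% | .405 | yes |
| 3 | 576/32768 = 1.8% | .481 | yes |
| 4 | 1941/32768 = 5.9% | .551 | no |

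Three is therefore the largest count inside the 2.5% tail. The Wilson bound alone (.274 × 15 = 4.1) would also let 4 through; the protocol's own .22 and the exact test do not.

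**4. How often each rule fires.** P(X ≤ c) for X binomial(15, p). Expected randomised = 100 × p × .90 or 100 × p × .80.

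| Prevalence p | Fewer than 3 (written) | 3 or fewer | Expected randomised per 100 assessed (10% / 20% loss) |
|---|---|---|---|
| .50 | 0.4% | 1.8% | 45 / 40 |
| .44 | 1.3% | 5.0% | 39.6 / 35.2 |
| .40 | 2.7% | 9.1% | 36 / 32 |
| .35 | 6.2% | 17.3% | 31.5 / 28 |
| .30 | 12.7% | 29.7% | 27 / 24 |
| .25 | 23.6% | 46.1% | 22.5 / 20 |
| .20 | 39.8% | 64.8% | 18 / 16 |
| .10 | 81.6% | 94.4% | 9 / 8 |

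The difference between the two rules is P(X = 3): 1.8 − 0.4 = 1.4 percentage points at .50, 29.7 − 12.7 = 17.0 at .30, and 64.8 − 39.8 = 25.0 at .20.

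**5. Prevalence needed for 40 from 100 assessed.** 40 / (100 × .90) = 44.4%, or 40 / (100 × .80) = 50%.

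**The case against.** The sentence that states the rule is true as written. Fewer than 3 of 15 does suggest a prevalence below .50 (0.4% probability at .50). What is wrong is using it as the trigger, because a count of 3 suggests the same by the protocol's own standard. The bound of .22 is also sound; only the step from bound to count fails.

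A reader might infer that the rule almost never fires when prevalence is too low to deliver 40 children. That is too broad. It holds for prevalences of about .35 to .44 (1% to 6%), but the rule fires 13% of the time at .30, 40% at .20 and 82% at .10.

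A reader might also infer that a missed trigger commits the pilot to a shortfall. The documents do not support this. The footnote in Section 4.4 is a second route to widening and does not depend on the 15-case look, although it has no threshold. The yields in the table assume exactly 100 assessments, whereas Section 6.2 treats 500 screened as a minimum, Section 6.1 treats two thirds agreeing to assessment as a minimum, Section 5.5 names further areas that could recruit, and Section 13.1 notes that sites can be added.

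A more sensitive cut-off, such as 5 or fewer, may look like the natural remedy. It is a trade-off and not a correction. The exact interval for 5/15 is 12% to 62%, so it cannot show a prevalence below .50. It would fire 15% of the time at .50 and 28% at .444, admitting sub-diagnostic children to a pilot that is meant to test whether enough diagnosed cases can be found.

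Finally, most of the low sensitivity comes from n = 15. With 3 or fewer, the look still fires only 9% of the time at .40 and 30% at .30. This stands, and it is why the probabilities should be stated.

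**Conclusion.** The point holds as a mismatch of one case between the stated bound and the trigger, in Sections 4.4 and 6.1 alike. The bound of .22 implies 3 or fewer; the text says fewer than 3. The written rule works at a 0.4% false-alarm rate where the correct reading gives 1.8%, and it loses detection of 6.3 percentage points at .40 (9.05 − 2.71), 17.0 at .30 and 25.0 at .20.

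The firing probabilities assume that the 15 assessed children are independent with a common prevalence. The yields further assume 100 assessments and a loss of 10% or 20%. The mismatch itself needs none of the yield assumptions: it follows from .22 × 15 = 3.3 and is confirmed by the exact test. No outcome analysis is affected.

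**What to change.** Change the trigger to 3 or fewer of 15 in the eligibility note in Section 4.4 and in the Pilot RCT part of Section 6.1. Beside the rule in Section 6.1, give the probability that it fires: 1.8% at .50, 9% at .40, 30% at .30 and 65% at .20. Add a sentence saying that a look at 15 cases has limited ability to detect prevalences of 30% to 44%, and that the footnote in Section 4.4 is the backstop for that range.

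The cost is one number in two places and a short addition. The statistical downside is a rise in the false-alarm rate from 0.4% to 1.8% at .50, and from 1.2% to 4.7% at .444. If the look has already been taken, the change alters the decision only if exactly 3 of the 15 children were diagnosed, and that count should be reported.
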